6.2 DATA ANALYSIS GENERAL CONSIDERATIONS

6.2.1 Definitions and Computations

Study day: Study day will be calculated in reference to the first dose date of study drug. First dose date of study drug is defined as the earliest date of the first dose of any study drug. For maintenance phase, C1D1 is the first dose date. For assessments conducted on or after the first dose date, study day will be calculated as (assessment date – first dose date of study drug + 1). For assessments conducted before the first dose date, study day is calculated as (assessment date – first dose date of study drug). There is no study day 0.

In the situation where the event date is partial or missing, the date will appear partial or missing in the listings. Study day and any corresponding durations will be presented based on the imputations specified in [Appendix 1](#).

Baseline: Unless otherwise specified, a baseline value is defined as the last non-missing value collected before the time of first dose.

Treatment Duration:

Arm A&B regular treatment period (with RT) is defined as date of the last non-zero dose of latest treatment – first dose date of earliest treatment +1; treatment duration

Arm A&B maintenance period is defined as last non-zero dose of latest treatment in maintenance phase – date of C1D1 of maintenance phase +1

Arm C is defined as date of last non-zero dose of latest treatment – first dose date of earliest treatment +1.

RANO assessments:

ORR (objective response rate) is defined as proportion of patients with best overall response of CR or PR per RANO criteria (confirmed by a subsequent tumor assessment at least four weeks apart). Best overall response will be assessed from the start of study treatment until data cut-off date, disease progression or start of new anti-cancer therapy. Patients without postbaseline tumor assessment are considered non-responders.

Modified DCR (disease control rate) is defined as the proportion of patients with CR, PR or SD per RANO criteria as the response assessment at the end-of-treatment (EOT) visit, as

scheduled per protocol. Patients with no EOT tumor assessment, as scheduled per protocol (due to any reason), will be considered non-responders for modified DCR.

DCR (disease control rate) is defined as the proportion of patients with best overall response of CR, PR or SD per RANO criteria. CR or PR will be confirmed by a subsequent tumor assessment at least four weeks apart.

CBR (clinical benefit rate) is defined as the proportion of patients with best overall response of CR, PR or SD \geq 24 weeks per RANO criteria. CR or PR will be confirmed by a subsequent tumor assessment at least four weeks apart.

BOR (best of response) is defined as the best response recorded from the start of study treatment until data cutoff, or start of new anti-cancer therapy. Computation of BOR will consider timepoints prior to PD when determining BOR.

Time to event data

OS (overall survival) is defined as the time from the first dose date to date of death for any cause. Patients that are still alive at the time of analysis will be censored at the last contact date that is known to be alive.

PFS (progression free survival) is defined as the time from the first dose date to disease progression per RANO criteria or death, whichever occurs first. Censoring rules for PFS are described in Table 1 in [section 6.4.2](#).

DOR (duration of response) is defined as the time from the date of the earliest documented response to disease progression or death for any cause whichever occurs earlier.

All calculations and analyses will be conducted using SAS version 9.4 or higher.

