4.1.1. Dose Escalation Phase (Phase 1b)

The Phase 1b, dose escalation phase consists of the following:

Arm A: Pamiparib (60 mg BID) administered continuously at increasing exposures of 2, 4, and 6 weeks in combination with RT administered for 6 to 7 weeks.

Arm B: Depending on the safety of the Arm A combination, the following combination may be explored: pamiparib (at the exposure determined as safe in Arm A) in combination with RT administered for 6 to 7 weeks and increasing doses of TMZ ([Section 4.2.1](#)).

In both Arms A and B, after RT is completed, patients will receive no further RT.

Maintenance Treatment for Arms A and B

Following completion of RT, at the discretion of the investigator and after discussion with the medical monitor, patients in the Arm A escalation and expansion and patients in Arm B escalation phases of the study may continue to receive pamiparib in combination with TMZ. TMZ will be given at a dose level lower than or equal to a dose that has been determined to be safe and tolerable in Arm C of study.

In the Arm B expansion phase of the study, maintenance treatment with pamiparib in combination with TMZ will be mandatory for all patients.

Dosing for this maintenance treatment should begin after the 4-week rest period (+ 7 days) to allow for recovery from RT treatment (please refer to [Appendix 1 Table 4](#)).

Arm C: Pamiparib (60 mg BID, administered continuously) in combination with increasing doses of TMZ ([Section 4.2.1](#)). TMZ will be administered on Days 1 to 21 of each 28-day cycle.

Approximately 60 patients may be enrolled in the 3 arms of the dose escalation phase. The actual sample size in this phase will depend on the number of dose escalation cohorts enrolled per arm.

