4.2. Details of Dose-Escalation Stage

4.2.1. Starting Dose and Dose-Escalation Approach

Arm A

RT will be administered QD × 5 days/week for 6 to 7 weeks with 1.8 or 2 Gy/fraction for a total target dose of between 58 Gy and 64 Gy.

The starting dose for pamiparib will be the 60 mg PO BID based on the rationale outlined in [Sections 1.3](#) and [1.4](#). In Cohort 1, exposure to pamiparib will be limited to the first 2 weeks of RT. In Cohorts 2 and 3, pamiparib will be given for the first 4 and 6 weeks of RT, respectively. If 2, 4, or 6 weeks of combination treatment exceeds the MTD, alternative regimens for pamiparib may be explored after discussions with all investigators based on which regimen exceeded the MTD and

what toxicities were observed. For example, if 2 weeks of pamiparib are not tolerated, a schedule of 1 week on, 1 week off, or 1 week on and 3 weeks off may be explored. Depending on data available at that time, a lower dose level of pamiparib may also be explored.

Arm B

The opening of Arm B will depend on the safety of the Arm A combination, and Arm B may be enrolled at the initial dose and schedule of pamiparib found to be safe and tolerable in Arm A. RT will be administered as for Arm A.

The first dose level of TMZ will be lower than or equal to a dose that has been determined to be safe and tolerable in Arm C, and dose escalation will proceed as described for Arm C. The time period of TMZ administration may be the same or shorter than that for pamiparib administration. Similar to Arms A and C, alternative regimens may be explored with adjustments of dose and/or schedule as outlined for Arms A and C.

Arm C

Since TMZ is given as a DNA-damaging sensitizer for pamiparib and to simplify TMZ dosing, flat-dosing will be used for TMZ. The first dose level of 40 mg QD corresponds to 23 mg/m^2 assuming an average body surface area of 1.73 m^2 . Subsequent dose levels of 80 mg and 120 mg correspond to 46 mg/m^2 and 69 mg/m^2 , respectively. Additional higher dose levels may be explored, and the TMZ dose will not be increased by more than 50% each time. TMZ will be given on Days 1 to 21 of each 28-day cycle based on data and rationale discussed in [Sections 1.2, 1.3, and 1.4](#).

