11.3.1. Extent of Exposure

Extent of exposure to each study treatment will be summarized in each arm descriptively as the number of cycles received (number and percentage of patients) in Arm C, duration of exposure (days), cumulative total dose received per patient (mg for pamiparib and TMZ and Gy for RT), dose intensity (mg/day for pamiparib and TMZ) and relative dose intensity.

The number (percentage) of patients requiring dose reductions, dose holds, and permanent drug discontinuation due to AEs will be summarized by arm. Frequency of dose reductions and study drug withholding will be summarized by categories.

Patient data listings will be provided for all dosing records and for calculated summary statistics.

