3 STUDY OBJECTIVES

3.1 PRIMARY OBJECTIVES

3.1.1. Phase 1b

Arm A (pamiparib + RT): Patients with first-line unmethylated GBM

- To assess safety and tolerability of pamiparib combined with RT
- To identify dose-limiting toxicities (DLTs) and determine the maximum tolerated dose (MTD) or maximum administered dose (MAD) and length of treatment for pamiparib combined with RT
- To select the recommended Phase 2 schedule for pamiparib combined with RT

Arm B (pamiparib + RT + TMZ): Patients with first-line unmethylated GBM

- To assess safety and tolerability of pamiparib combined with RT and TMZ
- To identify DLTs and determine the MTD or MAD for TMZ when combined with RT and the length of pamiparib treatment in combination with RT as determined in arm A
- To select the recommended phase 2 dose (RP2D) for TMZ when combined with RT and the length of pamiparib treatment as determined in arm A

Arm C (pamiparib + TMZ): Patient with recurrent/refractory GBM

- To assess safety and tolerability of pamiparib combined with TMZ
- To identify DLTs and determine the MTD or MAD for TMZ combined with pamiparib
- To select the RP2D for TMZ combined with pamiparib

3.1.2 Phase 2

Arm A, Expansion (pamiparib + RT): Patients with first-line unmethylated GBM

- To make a preliminary assessment of efficacy of pamiparib combined with RT followed by maintenance treatment of pamiparib + TMZ for those patients continuing onto maintenance treatment

Arm C, Expansion (pamiparib + TMZ): Patients with recurrent/refractory unmethylated or methylated GBM

- To make a preliminary assessment of efficacy of pamiparib combined with TMZ

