6.5.1 Extent of Exposure

Descriptive summaries will be provided by cohort and each arms for following variables:

- Number of cycles received (in arm C and in Arms A and B for maintenance patients)
- Treatment duration (days) for all arms (see section 6.2.1 for definitions)
- Number of patients require dose interruptions and reductions
- Total dose received per patient (mg for pamiparib and TMZ, and Gy for RT)
- Dose intensity (mg/day for pamiparib and TMZ) and relative dose intensity. Dose intensity per patient is defined as sum of actual dose received divided by planned duration of treatment. Relative dose intensity is defined as total actual dose received divided by total planned dose. Total planned dose is the total dose that would be delivered, if there were no modification to dose or schedule.

Patients with dose reductions and interruptions and the reasons for reductions and interruptions will be listed.

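### The SAP replaces the protocol's per-treatment duration of exposure with one regimen-level span, so in Arm A Cohorts 1 and 2 the duration summary largely reports the radiotherapy course

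*SAP*

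**What the plan says.** Protocol 11.3.1 sets the exposure analysis at the level of the component: "Extent of exposure to each study treatment will be summarized in each arm descriptively", and the items it then lists include duration of exposure in days.

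SAP 6.2.1 defines duration at the level of the regimen. For Arms A and B in the period with RT it is "date of the last non-zero dose of latest treatment – first dose date of earliest treatment +1". The definitions for maintenance and for Arm C have the same form. SAP 6.5.1 carries this into the exposure tables as "Treatment duration (days) for all arms (see section 6.2.1 for definitions") and names no other duration. The same section keeps total dose for each component, dose intensity, relative dose intensity, and the number of patients with interruptions and reductions, all by cohort and arm.

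In Arm A the quantity being escalated is time on pamiparib, "administered continuously at increasing exposures of 2, 4, and 6 weeks in combination with RT administered for 6 to 7 weeks" (Protocol 4.1.1). The SAP adds "length of treatment for pamiparib combined with RT" to the Arm A primary objective in its section 3.1.1. SAP 8, which lists departures from the protocol's planned analyses, does not mention duration of exposure.

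**The concern.** When components have different planned lengths, a span from the first dose of anything to the last dose of anything follows the longest one. In Arm A that is normally RT, which has the same planned length in every cohort, while pamiparib is planned for 2, 4 or 6 weeks. The duration row would then look much the same in cohorts that differ three-fold in the escalated exposure. It would also credit a patient who stopped pamiparib early with the full RT course. A reader of the study report who wants to know how long patients took pamiparib alongside RT would not find it in the row labelled duration, although the protocol planned to report it.

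**Working it through.** **Inputs**

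- Pamiparib, Arm A (Protocol 4.2.1): "In Cohort 1, exposure to pamiparib will be limited to the first 2 weeks of RT". The next two cohorts lengthen this to 4 and then 6 weeks. Planned days: 14, 28 and 42.
- RT (Protocol 7.1.3): 29 to 33 once-daily fractions, 5 days a week, up to 7 weeks.
- RT is given whatever happens to pamiparib (Protocol 7.1.3) and is modified only for events wholly or mainly due to RT (Protocol 7.1.5.2).
- Pamiparib dose levels (Protocol Table 3): 60, 40 and 20 mg twice daily, that is 120, 80 and 40 mg/day.

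Assumptions: RT and pamiparib both start on Day 1, fractions fall on Monday to Friday, and RT is not interrupted. The documents do not fix the start weekday, so all five are allowed.

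**Step 1. Length of the RT course.** The shortest case is 29 fractions from a Monday: five full weeks give 25 fractions by Day 35, and four more end on Day 39. The longest is 33 fractions from a Thursday: two fractions before the first weekend, then six full weeks from Day 5 give 30 more by Day 44, and the last falls on Monday, Day 47. The range of 39 to 47 days is 5.6 to 6.7 weeks, which agrees with the protocol's own figure of up to 7 weeks.

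**Step 2. The SAP duration.** With both components starting on Day 1, duration = max(last RT day, last pamiparib day) - 1 + 1.

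| Arm A cohort | Planned pamiparib days | SAP duration (days) | Excess over pamiparib (days) |
|---|---|---|---|
| 1 | 14 | 39-47 | 25-33 |
| 2 | 28 | 39-47 | 11-19 |
| 3 | 42 | 42-47 | 0-5 |

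**Step 3. An early stop in Cohort 3.** A patient who stops pamiparib on Day 14 and completes RT scores max(39 to 47, 14) = 39 to 47 days, close to a patient who took all 42 days.

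**Step 4. What the retained summaries recover.** Planned pamiparib totals are 14 x 120 = 1680 mg, 28 x 120 = 3360 mg and 42 x 120 = 5040 mg, so total dose does separate the cohorts. The Step 3 patient shows a relative dose intensity of 1680/5040 = 33%, so early stopping leaves a trace. Days on drug are not recovered, however. Take two Cohort 3 patients, ignoring hold days:

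- 28 days at 120 mg/day, then stopped: 3360 mg.
- 14 days each at 120, 80 and 40 mg/day: 1680 + 1120 + 560 = 3360 mg.

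Both have a relative dose intensity of 3360/5040 = 67%, with 28 and 42 days of pamiparib. The count of reductions would include the second patient but would not give the days for either.

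**Step 5. The dose-intensity denominator.** SAP 6.5.1 divides actual dose by planned duration of treatment without saying which treatment. For a fully dosed Cohort 1 patient, the pamiparib plan gives 1680/14 = 120 mg/day. A 42-day regimen, taken as an assumption, gives 1680/42 = 40 mg/day.

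**The case against.** The strongest reply is that this is one descriptive row in an otherwise adequate exposure analysis. Much of that stands.

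- A reader might infer that the SAP conceals pamiparib exposure altogether. It does not. Total dose, relative dose intensity, and interruptions and reductions are reported by cohort, and Step 4 shows that they carry real information. Nor is the combined span presented as pamiparib duration; it is labelled as the duration of treatment.
- A reader might infer that the Arm A primary objective can no longer be met. The documents do not support that. The schedule is chosen from dose-limiting toxicities under the modified 3+3 rules (Protocol 4.2.2 and 4.2.3, SAP 6.5.2), and a patient without such a toxicity needs at least 70% of scheduled pamiparib to be evaluable. The SAP also reports Phase 1b enrollment as complete at 46 patients, so this table could not steer escalation. The Phase 1b primary endpoints name dose intensity of each component, not duration.
- A reader might infer that the variable measures RT in every cohort. In Cohort 3 the two courses nearly coincide, and pamiparib may end last.
- A reader might extend the point with equal force to maintenance. Protocol 7.1.5.3 has pamiparib and temozolomide held together, which weakens it there, although Protocol 7.1.5.1 does foresee stopping one treatment alone.
- The Arm A and B definition in SAP 6.2.1 ends in a dangling phrase, so a clause may be missing or the text may have been damaged in extraction. The maintenance and Arm C definitions have the same form and are complete, which supports the reading used here.

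What does not stand is that the other rows make a component duration redundant. They do not return days on pamiparib, and the protocol planned to report those days.

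**Conclusion.** The point holds, limited to the duration summary. SAP 6.2.1 and 6.5.1 replace a per-treatment duration planned in Protocol 11.3.1 with a regimen-level one, and SAP 8 does not disclose it. Followed as written, the variable exceeds planned pamiparib time by 25 to 33 days in Arm A Cohort 1 and by 11 to 19 days in Cohort 2, and in Cohort 3 it masks only early pamiparib stops. These figures assume a common Day 1 start, weekday fractions and uninterrupted RT; an RT interruption would lengthen the span. Selection of the schedule and the efficacy results are not affected. The unspecified dose-intensity denominator is a related gap, and it matters more because dose intensity of each component is a Phase 1b primary endpoint.

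**What to change.** In SAP 6.2.1 and 6.5.1, derive duration separately for pamiparib, RT and temozolomide as the last non-zero dose of that component minus the first dose of that component plus 1. Do this within the RT period and again within maintenance, and tabulate each by cohort. State in SAP 6.5.1 that the dose-intensity denominator is the planned duration of the component concerned. Keep the combined span only as an additional row. The percentage of Arm A patients who completed their assigned pamiparib weeks would be a useful but optional addition, since the protocol does not ask for it. If the sponsor prefers the combined span alone, SAP 8 should list that as a change from Protocol 11.3.1.

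The cost is a few sentences of SAP text and a few table rows. The dosing records are already needed for the component total doses.

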6.2.2 Conventions

Unless otherwise specified, the following conventions will be applied to all analyses:

- 1 year = 365.25 days. Number of years is calculated as (days / 365.25) rounded up to 1 significant digit.
- 1 month = 30.4375 days. Number of months is calculated as (days / 30.4375) rounded up to 1 significant digit.
- Age will be calculated as the integer part of (first dose date – date of birth + 1)/365.25
- P-values will be rounded to 4 decimal places. P-values that round to 0.0000 will be presented as '< 0.0001' and p-values that round to 1.000 will be presented as '> 0.9999'.
- Duration of imaging-based event endpoints (such as PFS) will be based on the actual date the radiograph was obtained rather than the associated visit date.
- Missing efficacy or safety data will not be imputed unless otherwise specified.

- For by-visit observed data analyses, percentages will be calculated based on the number of patients with nonmissing data as the denominator, unless otherwise specified.
- For continuous endpoints, summary statistics will include n, mean, standard deviation, median, Q1, Q3 and range (minimum and maximum), unless otherwise specified.
- For discrete endpoints, summary statistics will include frequencies and percentages.

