DOR is defined as the time from the date of the earliest documented response (confirmed or unconfirmed) of CR or PR to disease progression or death for any cause, whichever occurs earlier. Only responders will be included in the DOR analysis. Censoring rule for DOR will follow PFS censoring rule.

Overall Survival (OS)

OS is defined as the time from the date of first study treatment to death of any cause. Patients who have not died by the analysis cutoff date will be censored at the last date known to be alive or the data cutoff date, whichever is earlier. OS will be performed for Safety Analysis Set.

Time-to-event variables PFS, OS and DOR will be estimated using the Kaplan-Meier (KM) method. KM estimates of PFS, DOR and OS will be plotted over time. Median PFS, DOR and OS, if possible to estimate, in each arm will be presented, along with their 2-sided 95% CIs using Brookmeyer and Crowley method (Brookmeyer & Crowley, 1982). The PFS-6m, PFS-12m, OS-6m, and OS-12m, defined as the proportion of patients in the Safety Analysis Set who remain alive and progression-free at 6 months and 12 months (or alive at 6 month and 12 months for OS), will be estimated using KM method along with the corresponding 95% confidence interval constructed using Greenwood's formula (Greenwood, 1926).

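### The SAP's month and year conversion rounds up to one significant digit; taken literally, any median OS, PFS or DOR above 10 and up to 20 months is reported as 20

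*SAP*

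**What the plan says.** The rule for months in SAP Section 6.2.2 is "Number of months is calculated as (days / 30.4375) rounded up to 1 significant digit". The rule for years is parallel: "Number of years is calculated as (days / 365.25) rounded up to 1 significant digit". The list opens with its scope: "Unless otherwise specified, the following conventions will be applied to all analyses".

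Two other items in the list matter. Age has a separate rule: "Age will be calculated as the integer part of (first dose date – date of birth + 1)/365.25". P-values are specified in different terms: "P-values will be rounded to 4 decimal places".

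SAP Section 6.4.2 defines the survival endpoints as times between dates, with no unit and no rounding rule; for example, "OS is defined as the time from the date of first study treatment to death of any cause". On reporting it says "Median PFS, DOR and OS, if possible to estimate, in each arm will be presented", with 95% confidence intervals. It also plans landmark rates: "The PFS-6m, PFS-12m, OS-6m, and OS-12m, defined as the proportion of patients in the Safety Analysis Set who remain alive and progression-free" at 6 and 12 months, or alive at those times for OS. It does not say whether the Kaplan-Meier input is in days or in rounded months, or whether the rounding is for display only. Protocol Section 11.2.5.2 gives no conversion or rounding rule either.

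**The concern.** One significant digit is not one decimal place. Below 10 months it leaves whole months (tenths below 1 month); above 10 it leaves only 10, 20, 30 and so on. Rounding upward then sends everything just above 10 to 20.

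The rule falls mainly on the survival endpoints. Most other durations in the SAP have their own unit: weeks for time since diagnosis and surgery (6.3.3), days for treatment duration (6.5.1), weeks for the stable-disease threshold in CBR (6.2.1). OS, PFS and DOR have no stated unit, and their landmarks are in months.

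At stake are the reported medians and their confidence limits and, depending on the order of operations, the 12-month rates. The study has no randomised control, so readers will set these figures beside outside data. An error that always lengthens survival would flatter the treatment.

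**Working it through.** The documents give no worked example that uses this rule, so there is no stated figure to reproduce. The conversion constant is consistent: 365.25 / 12 = 30.4375.

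**Inputs.** The rule comes from SAP 6.2.2. Illustrative values are taken from the unmethylated columns of protocol Table 1 (Section 1.2.3.2): OS of 8.8, 10.4, 11.8, 12.7 and 13.7 months and PFS of 4.4 months. They come from other studies and serve only as plausible magnitudes. Medians of 10 and 12 months are added as round assumptions.

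**Step 1: the rounding.** Rounding x up to one significant digit is ceil(x / 10^k) × 10^k, with k = floor(log10 x).

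- 4.4: k = 0, ceil(4.4) = 5.
- 8.8: k = 0, ceil(8.8) = 9.
- 10.4: k = 1, ceil(1.04) × 10 = 20.
- 11.8: ceil(1.18) × 10 = 20.
- 12.7: ceil(1.27) × 10 = 20.
- 20.3: ceil(2.03) × 10 = 30.

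So any median or confidence limit above 10 and up to 20 months shows as 20. Without censoring this is so whether rounding comes before or after the Kaplan-Meier step, because the rule preserves order.

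**Step 2: 12-month rates, only if rounded months are the Kaplan-Meier input.** Deaths after 10 and up to 12 months are moved to 20, so the estimate at 12 months becomes S(10). Assume exponential survival with median m and no censoring: S(t) = 0.5^(t/m).

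| Median m (months) | S(12), true | S(10), reported as 12-month rate | Difference (points) |
|---|---|---|---|
| 4.4 (PFS) | 0.5^(12/4.4) = 15.1% | 0.5^(10/4.4) = 20.7% | 5.6 |
| 8.8 | 38.9% | 45.5% | 6.6 |
| 10 | 43.5% | 50.0% | 6.5 |
| 10.4 | 44.9% | 51.4% | 6.5 |
| 11.8 | 49.4% | 55.6% | 6.2 |
| 12 | 50.0% | 56.1% | 6.1 |
| 12.7 | 51.9% | 57.9% | 6.0 |
| 13.7 | 54.5% | 60.3% | 5.8 |

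A simulation of 200,000 exponential times agrees. At median 10.4 the 12-month rate moves from 44.8% to 51.1%, and at median 12.7 from 52.0% to 57.9%. Both rounded medians are 20.

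**Step 3: 12-month rates if the input is days.** No time is moved, so OS-12m and PFS-12m are unchanged.

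**Step 4: 6-month rates.** Between 1 and 10 months the rule rounds up to whole months, so no time crosses 6. OS-6m and PFS-6m are unchanged under either order; the simulated values were identical before and after rounding.

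**Step 5: the one-decimal reading.** Rounding up to a tenth moves a time by less than 0.1 month (0.1 × 30.4375 = about 3 days) and by about 0.05 month on average (about 1.5 days). For example, 317 days is 10.41 months, which becomes 10.5 rounded up and 10.4 rounded to nearest. No time crosses 6 or 12 months, so the landmark rates do not move.

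**The case against.** The strongest reply is that the literal reading is not what was meant. A month scale that cannot separate 11 from 19 months makes no sense in a plan that reports medians with 95% confidence intervals and 12-month rates. The phrase is most likely a slip for one decimal place. That is a fair inference, and I share it, but the SAP does not say so. The same list uses decimal places for p-values, and the month rule is worded as a calculation, with nothing limiting it to display. A programmer must either follow it and misreport the medians or depart from it without a record.

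A reader might go further and infer that OS-12m and PFS-12m are wrong as the plan stands. The documents do not support that. The endpoints are defined between dates, and no passage says that rounded months enter the Kaplan-Meier estimate. The scope sentence allows that reading but does not establish it, so the figures in Step 2 are conditional.

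A reader might also infer that every time in months or years is affected. That is too broad: age follows its own integer rule, and several other durations are in days or weeks.

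Finally, the primary endpoints, modified DCR and ORR, are proportions that do not use this rule. OS, PFS and DOR are secondary and descriptive, with no test attached, and no sample size or decision rule depends on months. This stands and limits the severity.

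**Conclusion.** The point holds as a minor correction to an operative rule that is wrong as written. The effect on medians and confidence limits needs only literal application: values above 10 and up to 20 months are reported as 20. The effect on OS-12m and PFS-12m, about 6 to 7 points, needs two further things: rounded months as the Kaplan-Meier input, and survival close to exponential with little censoring. Under the probable one-decimal intent, what remains is an upward shift of about 0.05 month on average.

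It would be too strong to conclude that the trial's survival results will be wrong. The documents show a defective rule, not how it was programmed. Confidence is high on the wording and the arithmetic; the landmark bias is a possibility only.

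**What to change.** Replace the month and year rules in SAP Section 6.2.2 with: *Time-to-event analyses use unrounded days; results are converted to months (days/30.4375) or years (days/365.25) for display and rounded to the nearest 1 decimal place; age keeps its own integer rule.*

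This settles the number of digits, the direction of rounding and the order of operations. It costs one sentence, needs no new data and involves no trade-off. Any survival outputs already programmed should be checked for where the rounding takes place.
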